## 1. Introduction

This protocol covers two experiments (experiments 2 and 4) that form part of a larger project entitled Physiological Flow of Liquids Used in Dysphagia Management. The project has been submitted to the National Institutes of Health for R01 funding, and has scored at the 9th %ile. Confirmation of funding is expected by October, 2015.

The overall goal of the project is to collect measurements of liquid flow through the oropharynx (i.e., mouth and throat) during swallowing. The factors that are expected to influence liquid flow include the liquid consistency (i.e., thin, slightly-thick, mildly-thick, moderately-thick, extremely thick) and the forces applied during swallowing (i.e., tongue pressures and swallowing muscle contraction). The objective is to determine how these factors interact to influence the flow of a liquid through the oropharynx, both in healthy adults and in adults who have swallowing impairment.

Experiments 1 and 3 of the project involve basic science bench experiments, in which we will develop and test the liquid stimuli for use in the subsequent human subject experiments.

Experiments 1 and 3 involve collaboration with co-investigators [name] (University College London) and [name] (University of Guelph) and consultant [name] (University of Toronto, Mechanical Engineering).

Experiments 2 and 4 (which comprise the focus of this protocol) will use the liquids developed in experiments 1 and 3 and collect measures of liquid flow and swallowing behaviour in healthy adults, i.e., those with no known swallowing impairment. Experiments 2 and 4 will take place at the Swallowing Rehabilitation Research Lab of the Toronto Rehabilitation Institute.

Videofluoroscopy x-rays for Experiment 2 will be conducted on a purchased service basis in the diagnostic imaging department at the Toronto General Hospital.

Experiment 5 (for which a separate protocol will be submitted at a later date) will collect the same measures of liquid flow and swallowing behaviour in adults with swallowing impairment due to 5 different etiologies, and will be a multi-site study involving co-investigators [name] (Toronto Rehabilitation Institute – Brain and Spinal Cord Program), Drs. [name] and [name] (Toronto Rehabilitation Institute – Lyndhurst Centre – Brain and Spinal Cord Program), Drs. [name] and [name] (Princess Margaret Hospital Head and Neck Cancer Centre) and [name] (University of Florida, Gainesville).

## 2. Steering Committee

In addition to the PI, co-investigators and consultants named above, [name] and [name], who are co-chairs of the *International Dysphagia Diet Standardisation Initiative* ([www.idssi.org](http://www.idssi.org)) will serve as consultants to the project. Together, this team of 12 key personnel will form the steering committee for the project. An annual face to face meeting and quarterly teleconference calls are planned for study oversight and progress review.

## 3. Purpose and Specific Aims

Dysphagia (swallowing impairment) is a serious condition, involving two primary functional concerns:

- 1) the ability to swallow safely, without material entering the airway (penetration-aspiration);
- 2) the ability to swallow efficiently, without leaving residue behind in the pockets of the pharynx.

Impaired swallowing safety is linked to pneumonia while impaired efficiency contributes to risk of malnutrition. Dysphagia is estimated to affect 6.7% of hospital admissions in the USA with an annual attributable cost of \$547 million. Dysphagia is common in the elderly and in individuals with stroke, brain injury, head and neck cancer, cervical spine injury or surgery, and developmental or neurodegenerative conditions. When an individual presents with dysphagia, the most common intervention is to alter the consistency of the foods and fluids they consume. Thicker liquids flow more slowly (making them easier to control and making penetration-aspiration less likely). Pureed/ minced/soft foods are thought to be easier to transport than unaltered solid foods. **Despite the simplicity of these ideas, we lack evidence to guide the modification of food and liquid textures for clinical benefit.**

The National Dysphagia Diet, a guideline that is currently in use in the USA, describes four levels of liquid consistency: *thin, nectar-, honey- and spoon-thick* liquids. Although viscosity ranges are proposed for these categories, these lack empirical evidence. **Viscosity measurement is complex and not practical for caregivers, clinicians or institutional kitchens to perform.** A recent systematic review published by the *International Dysphagia Diet Standardisation Initiative* (IDDSI) concluded, “**there is a need to classify food and fluid behavior in the context of the physiological processes involved in oral transport and flow initiation**”. We propose to take up this challenge with a pivotal and comprehensive study **to determine physiological-rheological correlates (i.e. bolus flow and swallowing kinematics) across a continuum of liquid consistency in healthy and disordered swallowing.** To do this, we will prepare starch- and gum-thickened liquids in 5 consistencies (*Level 0 - thin, Level 1 - slightly-thick, Level 2 - mildly-thick, Level 3 - moderately-thick and Level 5 - extremely-thick*) according to the IDDSI framework. Operational definitions for these consistencies have been developed by

IDDSI based on gravity-flow tests (i.e. practical tests that can be used to verify consistency at the time of preparation). The IDDSI gravity-flow testing method is illustrated in Appendix A. Experiments 1 and 3 will be basic science experiments to confirm the flow properties of these liquids and to identify barium and non-barium liquids with matching flow properties. In experiments 2, 4 and 5 we will use these liquids and collect time-linked videofluoroscopic measures of bolus flow and physiological measures of swallowing behavior (i.e. tongue pressures and submental muscle contraction patterns) **to determine the dose-response pattern of progressive increments of liquid thickening in adults with and without dysphagia.**

We have three specific aims, the first two of which will be addressed in this protocol:

**Aim 1: To determine the relationship between bolus flow and healthy swallowing physiology.** In Experiment 2, we will collect concurrent videofluoroscopic and physiological measures of swallowing (tongue pressure, electromyography [sEMG], nasal airflow) in healthy adults using barium stimuli across the continuum of liquid consistency. Significance: This will show the impact of consistency on bolus flow through the oropharynx, controlling for the forces used to initiate flow and propel the bolus.

**Aim 2: To compare healthy swallowing physiology for barium versus non-barium stimuli.** In Experiment 4, we will collect physiological measures of swallowing using barium and non-barium stimuli matched for consistency. Significance: This will determine how swallowing behaviors (tongue pressures, sEMG, nasal airflow, tracheal sounds and accelerometry, where captured) differ between barium and non-barium stimuli with matched consistency, enabling us to develop models of flow accounting for these differences.

**Aim 3: To explore the relationship between bolus flow and swallowing physiology in dysphagia.** In a future planned experiment (Experiment 5), we will collect concurrent videofluoroscopy and physiological measures of swallowing in adults with dysphagia using barium stimuli across the continuum of liquid consistency. We will study 5 groups in whom dysphagia is common: stroke; acquired brain injury; oropharyngeal cancer; cervical spine surgery/injury; and neuro-degenerative disease. Significance: This will enable us to identify the boundaries of *ideal* thickening (i.e., *not too thin* and *not too thick*), based on swallowing pathophysiology (altered pressure and force generation capacity).

## 4. Methods

### *Participants:*

Experiments 2 and 4 will involve the participation of a single sample of participants in the following sub-groups:

i) 40 healthy adults, aged under 60 years old, recruited from the Toronto population at large;

ii) 40 healthy adults, aged over 60 years old, recruited from the Toronto population at large;

Participants will be asked to complete both experiments. Recruitment for Experiment 4 was terminated on July 24 2018 due to technical issues encountered with the equipment that could not be repaired by the manufacturer. The target age ranges for the age sub-groups in Experiments 2 and 4 have been selected based on our previous research, which suggests that significant age-related differences in tongue pressures in swallowing are detectable over the age of 60. We will recruit an equal number of male and female participants within each age-group. Participants of all ethnic and racial groups will be accepted, however adequate comprehension of the English language consent documents will be required.

### *Exclusion Criteria:*

- The healthy adult participants for Experiments 2 and 4 will be accepted into the study, provided that they have no prior history of swallowing, motor speech, gastro-esophageal or neurological difficulties, chronic sinusitis or taste disturbance.
- Individuals with a history of surgery to the speech or swallowing apparatus (other than routine tonsillectomy or adenoidectomy) will be excluded.
- Similarly, due to the requirement to swallow stimuli containing starch based thickeners, which carry a significant carbohydrate load, individuals with Type 1 Diabetes will be excluded.
- Due to the fact that neurological impairments comprise an exclusion criterion, individuals with cognitive communication difficulties that may hinder comprehension of the study documents will be excluded from this study.
- Individuals with known allergies to latex or medical adhesive will be excluded, due to the probability that these items will come into contact with the oral mucosa, neck, and chin areas during data collection.
- As a further precaution due to the use of radiation in experiment 2, we will exclude women who report current pregnancy and individuals who report that they have had an x-ray to the neck in the past 6 months.
- Finally, individuals who report that they are occupationally exposed to radiation will be advised that they should not participate if they believe their occupational radiation exposure may exceed half the allowed Ontario annual limit of 20 mSv.
- These exclusion criteria will be confirmed using a self-report questionnaire form at the time of intake into the study (see Appendix B). Any questions will be clarified through

discussion with the research assistant responsible for participant intake, and, where necessary with the principal investigator.

Children will not be involved in this protocol due to the use of radiation. Although the research questions are of interest for all ages, including children, we feel that it is most appropriate to answer the current research questions in adults before considering whether similar studies should be repeated in children. In particular, the variety of physiological variation we detect in both healthy adults and those with dysphagia will help to determine whether a future study involving healthy children requires videofluoroscopy to establish a healthy reference perspective.

*Recruitment:*

Recruitment of participants for Experiments 2 and 4 will be conducted in two ways:

- 1) We will request permission to contact individuals who have registered with the Toronto Rehabilitation Institute research volunteer database, who have agreed to be contacted for future studies and who meet the broad inclusion criteria of the study.
- 2) We will conduct a broad public advertising campaign through local newspapers, magazines, a web-site, mailings and posters at community centres, seniors' residences, places of worship, and around the University of Toronto and the Toronto Rehabilitation Institute. In particular, we anticipate advertising in a seniors' magazine (*50Plus*) and its associated website, which has been useful in previous studies. Participants will be required to attend a 1-hour intake appointment to confirm their eligibility to participate, introduce them to the research protocol, complete the intake questionnaire, and obtain informed consent (see attached consent documents in Appendices C and D).

*Stimuli:*

Prior to launching Experiments 2 and 4, we will develop an array of barium (Experiment 1) and non-barium (Experiment 3) stimuli in thin, slightly-thick, mildly-thick, moderately-thick and extremely-thick consistencies, defined using the International Dysphagia Diet Standardisation Initiative (IDDSI) gravity-flow measures. The barium stimuli will be prepared using E-Z-Paque® barium in 20% w/v barium concentration with starch and gum-based thickening agents (Nestlé Resource® ThickenUp® and ThickenUp Clear®). The non-barium stimuli will be prepared using Nestlé® Pure Life® Splash, a mildly lemon-flavored water. Starch and gum-based thickening agents will be added to match the flow characteristics of the barium stimuli developed in Experiment 1. Experiments 1 and 3 will produce two arrays (barium; non-barium) of starch- and gum-thickened liquids representative of each IDDSI flow level, for a total array of 1 thin and 8 thickened stimuli (4 gum; 4 starch).

All stimuli will be prepared in the Swallowing Rehabilitation Research Laboratory not longer than 6 hours prior to scheduled use, according to a strict standard operating procedure (see

Appendix D). Barium stimuli will be transported to the radiology suite at Toronto General Hospital in a cooler, as per routine clinical procedures.

*Data to be collected from each participant:*

The following types of data will be collected from participants in Experiments 2, and 4:

- a) An intake questionnaire noting age, sex, ethnicity and race data and confirming eligibility based on the absence of reported exclusion criteria.
- b) During the intake process, we will ask to review a list of conditions that could alter the results of the research study and identify whether any of these conditions apply. This disclosing the use of any medications that they are currently taking, in order to allow us to control for the possible influence of medication on oral sensory and motor function. Medications do not qualify as the basis for exclusion. However, it is important for us to collect information regarding the use of benzodiazepines and neuroleptic medications that are known to have possible effects on swallowing, particularly with respect to causing xerostomia (dry mouth).

*Signals to be collected from each participant:*

- c) Tongue-pressure waveform data, using the hand-held Iowa Oral Performance Instrument (IOPI) will be collected at the anterior position during 3 anterior maximum presses and 3 saliva swallows.
- d) Nasal airflow collected using nasal cannula and registered on the KayPENTAX Swallowing Signals Lab during swallows.
- e) A videofluoroscopy recording of swallowing involving a pulse rate of 30 pulses per second and video capture at 30 frames per second.

*Data Collection Procedures:*

Experiment 2: Prior to data collection, a nasal cannula will be placed around the participant's head with flexible prongs resting in their nostrils to measure airflow.

A single use disposable tongue bulb for the hand-held Iowa Oral Performance Instrument (IOPI) will be placed inside the participant's mouth. Tongue pressure signal will be collected at the anterior position during 3 anterior maximum presses and 3 saliva swallows.

[figure not shown]

Image 1. Tongue pressure sensors.

Following sensor attachment, the participants will be seated on a chair inside the fluoroscopy unit. The video output line from the fluoroscopy unit and the nasal cannula will then be connected to the KayPENTAX Digital Swallow Workstation Swallowing Signals Lab equipment,

which is located on a properly insulated cart with an uninterrupted power supply and isolation transformer.

Participants will be asked to swallow the barium stimuli developed in Experiment 1 (9 in total) in videofluoroscopy, with concurrent measurement of nasal airflow. Videofluoroscopy will be performed at maximum temporal resolution (30 pulses/second) and captured at 30 frames/second. Each stimulus will be presented twice, in a randomized block design.

Participants will be allowed to take natural sized sips of each stimulus from cups containing 40 ml. Cup weights before and after each sip will be taken on a digital balance so that sip volume and mass can be calculated.

Experiment 4: Experiment 4 was terminated on July 24 2018 due to technical issues encountered with the equipment that could not be repaired by the manufacturer.

*Data Processing:*

Signals collected from the participants (which may include tongue-pressure, sEMG, nasal airflow, tracheal sounds and accelerometry waveform data) will be segmented using an automatic segmentation algorithm developed previously in the PI's lab. Similarly, the videofluoroscopy recordings will be spliced into single bolus clips and the audio channel will be muted to remove cues that might bias rating. Blinded videofluoroscopy rating will then be performed in duplicate by trained raters in the [name] Lab following established procedures (see Appendix E). Discrepancies between raters will be flagged and resolved at consensus meetings, as required. These procedures will yield a large number of parameters for each swallow, as listed below:

- a) Peak tongue-pressure amplitude (in mm Hg);
- b) Rise-time to peak tongue-pressure (in ms);
- c) Decay-time for tongue-pressure (in ms);
- d) Tongue-pressure area-under-the-curve;
- e) Peak sEMG amplitude (in  $\mu$ V);
- f) Rise-time to peak sEMG amplitude (in ms);
- g) Decay-time for sEMG (in ms);
- h) sEMG area-under-the-curve;
- i) Duration of apnea (ms);
- j) Breathing pattern pre- and post- swallow;
- k) Bolus transit time from ramus of mandible to vallecular pit (in ms);
- l) Bolus dwell time in pharynx from ramus of mandible to laryngeal vestibule closure (in ms);

- m) Pharyngeal bolus transit time from ramus of mandible to upper esophageal sphincter opening (in ms);
- n) Bolus transit time from ramus of mandible to tail exiting the upper esophageal sphincter (in ms);
- o) Amount of residual left behind in the valleculae and pyriform sinuses after the initial swallow (measured using the Normalized Residue Ratio Scale;
- p) Number of swallows for the bolus.

*Data Analysis:*

We will model the impact of bolus consistency on videofluoroscopic measures of pharyngeal bolus flow (i.e., the interval from the bolus passing the mandibular ramus until laryngeal vestibule closure; pharyngeal transit time) and post-swallow residue (Normalized Residue Ratio Scale). The analyses for Experiments 2 and 4 will involve linear mixed model ANOVAs with repeated measures. A path analysis approach will be used to first identify differences in tongue-pressure and submental sEMG measures (amplitude, rise time, decay time) across stimuli. The influence of variations in bolus volume will also be explored using univariate tests, and, if confirmed to be significant, will be used as a covariate in the subsequent statistical models. Similarly, differences in the dependent variables as a function of sex or age (continuous or divided into groups) will be explored first in a univariate fashion, and, if significant, these between-participant factors will be included in the model.

For Experiment 2, **our main hypothesis is that liquids with similar gravity-flow properties will show similar pharyngeal bolus flow.** Our goal will be to detect differences in bolus flow measures  $\geq 200$  ms as a function of consistency, with a medium effect size (Cohen's  $d \geq 0.5$ ). We hypothesize that the healthy participants in these experiments will use higher amplitudes of tongue pressure and/or submental muscle contraction (sEMG) during oral propulsion of starch-thickened stimuli, thereby achieving a similar outcome for both starch- and gum-thickened liquids in terms of pharyngeal bolus flow. Model fit for different covariance structures will be explored using restricted log likelihood estimation. Age-group (< vs.  $> 60$  years) will be used as a between-groups factor while bolus consistency will be used as the within-participants factor. Sample size calculations have been performed using the data from the PI's previous grant, in which ultrasound measures of the duration of hyoid movement differed by 200-400 ms between age-groups and tongue-pressure amplitudes varied by 10-35 mm Hg depending on the liquid studied. A power calculation shows that 36 participants per group will be needed to detect this difference with 80% power ( $\alpha=0.05$ ). Allowing a margin for attrition, we have therefore planned to enroll  $n=40$  per participant group: total  $N=80$  for Experiments 2 and 4. This sample size will also be adequately powered for Experiment 4 to detect differences  $\geq 10$  mm Hg in tongue-pressure amplitudes.

For Experiment 4, **our main hypothesis is that liquids with similar flow properties based on the IDDSI gravity-flow tests will elicit different tongue pressure and sEMG measures based on their actual viscosities.** This hypothesis is predicated on the idea that healthy adults modulate oral phase propulsive forces used for boluses of differing consistency with the goal of establishing uniform pharyngeal flow (as hypothesized for Experiment 2). Significant contrasts are expected between the two extremes of the liquid continuum: [*thin* and *slightly-thick*] vs. [*moderately-* and *extremely-thick*]. We expect that measures for the *mildly-thick* liquids will fall in between, but that differences may not be large enough to achieve statistical significance versus the extremes in pairwise comparisons. We predict that barium stimuli will elicit higher amplitudes of tongue-pressure than non-barium stimuli based on their increased density.

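### Experiment 2 as now described records tongue pressure and sEMG on none of its 18 barium boluses, so the planned force analyses have no data

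*Combined protocol and SAP*

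**What the plan says.** Aim 1 (section 3) says of Experiment 2 that "we will collect concurrent videofluoroscopic and physiological measures of swallowing (tongue pressure, electromyography [sEMG], nasal airflow) in healthy adults". It gives as the purpose the effect of consistency on flow, "controlling for the forces used to initiate flow and propel the bolus".

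Section 4, Data Analysis, says that a path analysis "will be used to first identify differences in tongue-pressure and submental sEMG measures (amplitude, rise time, decay time) across stimuli". It then hypothesizes that healthy participants push harder, by tongue pressure or submental contraction, on starch-thickened stimuli, and that this is how starch and gum come to flow alike. Data Processing lists 16 parameters for each swallow. Items a to d are tongue pressure and items e to h are sEMG.

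The collection text in section 4 is narrower. The list of signals collected from each participant has three entries: IOPI tongue pressure, nasal airflow and videofluoroscopy. The Experiment 2 procedure says: "Tongue pressure signal will be collected at the anterior position during 3 anterior maximum presses and 3 saliva swallows". Only the fluoroscopy video line and the nasal cannula are then connected to the recording workstation. On the boluses themselves: "Participants will be asked to swallow the barium stimuli developed in Experiment 1 (9 in total) in videofluoroscopy, with concurrent measurement of nasal airflow". sEMG is not mentioned in the signal list or the procedure. Section 7 schedules two appointments, intake and videofluoroscopy.

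**The concern.** The analysis and hypothesis text presumes that force is measured on each bolus, and the procedures no longer measure it there. If the plan is followed exactly, one named analysis step, one stated hypothesis and one clause of Aim 1 have nothing to work on.

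The practical risk lies in interpretation. The main Experiment 2 hypothesis predicts similar flow for liquids with similar gravity-flow results, and the plan supplies the explanation in advance: extra effort on starch. If starch and gum flow do look alike, that explanation is ready to be adopted although no force was recorded. Equal flow with equal effort and equal flow through compensating effort are different findings, and filmed flow alone cannot tell them apart.

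**Working it through.** **Boluses per participant.** The Stimuli text gives 1 thin, 4 gum and 4 starch stimuli, so 1 + 4 + 4 = 9, which matches the 9 stated in the Experiment 2 procedure. Each is presented twice:

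- all boluses: 9 × 2 = 18
- thickened: 8 × 2 = 16 (starch 4 × 2 = 8, gum 4 × 2 = 8)
- thin: 1 × 2 = 2

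**Signals set against those boluses, under the current procedures.**

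| Signal | Barium boluses with data | Basis |
|---|---|---|
| Videofluoroscopy | 18 of 18 | stated |
| Nasal airflow | 18 of 18 | stated as concurrent |
| Tongue pressure | 0 of 18 | occasions listed: 3 presses, 3 saliva swallows |
| sEMG | 0 of 18 | absent from signal list and procedure |

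Eighteen is the planned maximum. A session can end early under section 5 (the 3-minute exposure bell, or aspiration). These are counts of boluses, not swallows, because one bolus may take several swallows (parameter p).

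**What the path step needs.** It names 3 features (amplitude, rise time, decay time) of 2 signals, so 3 × 2 = 6 measures. None of the 6 is available on barium boluses. Of the 16 listed parameters, 4 + 4 = 8 (a to h) are unavailable for barium boluses and 8 (i to p) remain. The starch-versus-gum force contrast has data on 0 of 8 starch and 0 of 8 gum boluses.

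**Can the saliva-swallow and maximum-press values stand in?** They form one set per participant and do not change from stimulus to stimulus. They therefore cannot show differences across stimuli. In balanced data they also cannot adjust a within-participant consistency contrast, because a covariate that is constant within a participant is orthogonal to it. A simulation with assumed means and variances (80 participants × 18 boluses, mixed model with and without such a covariate) changed the consistency contrasts by less than 1e-11 ms.

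**What the main model needs.** Its outcomes are filmed flow times and the residue ratio. Its stated terms are consistency, age group, and volume, sex or age where significant. No force term is listed, so it can be fitted from the data collected.

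**Upper bound.** If all 80 planned participants were studied this way, 18 × 80 = 1,440 boluses would carry no force data. Tongue pressure would exist for at most 3 × 80 = 240 saliva swallows and 240 maximum presses, none involving a stimulus. The documents do not say how many participants were studied this way.

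**The case against.** The strongest reply is that the data may exist elsewhere. Of the other experiment the protocol says: "In Experiment 4, we will collect physiological measures of swallowing using barium and non-barium stimuli matched for consistency". Participants were asked to complete both experiments, the starch-effort hypothesis is worded for both, and Data Analysis gives the direct test of force differences to Experiment 4. Participants who finished it before it was terminated on July 24 2018 may have force data by bolus. This stands, and it is why the conclusion is limited to participants studied under the current Experiment 2 procedures. It does not restore Aim 1: no videofluoroscopy is described for Experiment 4, so its signals can be linked to filmed flow only by participant and stimulus, not swallow by swallow.

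A second reply is that the text already makes these signals optional. Data Processing lists tongue pressure and sEMG among signals that might be present, and the budget justification covers a workstation for all physiological signals in both experiments, plus EMG sensors. The Experiment 2 procedure also refers to sensor attachment. None of this adds a procedure that records force on a barium bolus. It does weaken the sEMG count, which rests on absence from the procedures; no sentence says that sEMG is not recorded.

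A third reply is that calling the main flow analysis unaffected goes too far, since Aim 1 defines the consistency effect as adjusted for force. This is fair. The model as specified can be estimated, but its result is not force-adjusted, and the plan does not say whether the path step was meant to feed force measures into it.

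**Conclusion.** The concern holds. Under the current Experiment 2 procedures, tongue pressure and sEMG are recorded on 0 of 18 barium boluses per participant. For participants studied this way, the path-analysis step (6 of 6 measures missing on barium boluses), the starch-effort hypothesis and Aim 1's force adjustment cannot be estimated. The similar-flow hypothesis and the mixed model of consistency on flow and residue can still be addressed, without adjustment for force.

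This rests on reading the signal list and procedure as complete. That reading is explicit for tongue pressure and inferred for sEMG. The number of participants with bolus-level force data is not given. No power can be worked out for that subset, because the plan gives a 10 mm Hg target with no standard deviation or effect size for the force contrast. The point should be fixed, but it does not undermine the main analysis.

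**What to change.** Reconcile Aim 1, Data Processing and Data Analysis with the Experiment 2 procedures and the visit schedule in section 7:

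- Limit the path step, the starch-effort hypothesis and bolus-level use of parameters a to h to participants with bolus-level tongue pressure or sEMG, and report how many there are. If there are none, withdraw these items.
- State that Experiment 4 signals link to filmed flow only by participant and stimulus.
- Bring Aim 1's list of concurrent measures and its force-adjustment clause into line with what is recorded.
- State that similar starch and gum flow will not be attributed to compensating effort in participants without force data.
- Keep tongue pressure from saliva swallows, if wanted, as a participant-level measure and not as the force applied to a bolus.
- Keep the mixed model of consistency on flow and residue as written, and state that it carries no force term.

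The cost is protocol and analysis wording plus one count. The mechanistic claim is lost or confined to a subset of unknown size. This assumes that Experiment 2 continues as described. The documents report an equipment failure for Experiment 4 only and do not say whether force recording on barium boluses could be restored in Experiment 2. If it were, the procedures would have to say so.
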